13. SAFETY

Safety endpoints will be analyzed using the Safety population. Safety endpoints will be summarized descriptively as described in section 3.1.

13.1 Adverse Events

All AEs including will be coded using MedDRA. All AE summaries will be restricted to TEAEs only. Summary tables will include the number of participants (%) experiencing an event and the number of events. Participants will be counted only once for each SOC and PT level (categorical descriptive analysis).

AE and SAE will be analysed taking into account any identified subject with Sars-Cov2 infection during and post-pandemic measures phases. Such an analysis will be operated through the independent Data Monitoring Committee (DMC).

The TEAE summaries will include:

- Overall summary of TEAEs.
 - Number of TEAEs
 - Number of TEAEs with Severity \geq Grade 3 Severe
 - Number of Serious TEAEs
 - Number of Study Drug Related TEAEs (Drug Related: A Possibly, Probably or Definitely related TEAE)
 - Number of Entecavir (ETV) Related TEAEs (Drug Related: A Possibly, Probably or Definitely related TEAE)
 - Number of Tenofovir Disoproxil Fumarate (TDF) Related TEAEs (Drug Related: A Possibly, Probably or Definitely related TEAE)
 - Number of TEAEs leading to study drug withdrawal
- TEAE summary by SOC and PT.
- TEAE summary of serious events by SOC and PT.
- TEAE summary by SOC, PT and Severity.
- TEAE summary by SOC, PT and relationship to study drug.
- TEAE summary by SOC, PT and relationship to ETV.
- TEAE summary by SOC, PT and relationship to TD.
- TEAE summary of events leading to the study drug discontinuation by SOC and PT.

All AEs will be listed and will include verbatim term, PT, SOC, treatment, causality to study drug, ETV and TDF, severity, seriousness, outcome, and action taken with regards to the study drug and AE. Separate listings will be created for SAEs and events leading to study drug withdrawal.

13.2 Safety Laboratory Assessments

Blood and urine samples will be collected at the time points specified in the Schedule of Events (refer to the Protocol) to conduct hematology, chemistry, coagulation, lipid and metabolic profile and urinalysis (including microscopic examinations) analyses.

The following tests will be performed within each of the specified test panels:

Hematology:

- Red blood cell count
- White blood cell count

- Haemoglobin
- Haematocrit
- Partial automated differentiation
 - Thrombocytes (% and Abs)
 - Lymphocytes (% and Abs)
 - Monocytes (% and Abs),
 - Eosinophils (% and Abs),
 - Basophils (% and Abs),
 - Neutrophils (% and Abs)
 - Platelets (% and Abs).

Coagulation:

- Prothrombin Time (s)
- INR
- Activated Partial Thromboplastin Time
- Fibrinogen

Serum Chemistry:

- Albumin
- ALP
- ALT
- Amylase
- Apo A1
- AST
- AST/ALT ratio
- Bilirubin conjugated (direct bilirubin)
- BUN
- Calcium
- Creatine Kinase
- Creatinine phosphokinase (CPK)
- Creatinine
- C-Reactive Protein-hs
- Estimation of glomerular filtration rate
- GGT
- Glucose
- Insulin
- Lactate dihydrogenase
- Potassium

- Sodium
- Total Bilirubin (if >ULN, add conjugated bilirubin)
- Total Protein
- Uric Acid

Lipid Metabolic Profile

- Cholesterol
- Branched-chain amino acid concentrations as liver function test, (analyze done by Labcorp)
- Haemoglobin A1c,
- Homeostatic model assessment for insulin resistance (morning fasting glucose and insulin),
- Lipoprotein insulin resistance index by nuclear magnetic resonance based on serum cholesterol (analyze done by Labcorp),
- HDL-C (analyze done by Labcorp),
- LDL-C (analyze done by Labcorp),
- Triglycerides (analyze done by Labcorp),
- Apolipoprotein B,
- Small dense LDL (analyze done by Labcorp),

Urinalysis (Dipstick) & Microscopic Urinalysis:

- Blood
- Bilirubin
- Glucose
- Ketones
- Leukocytes
- Haemoglobin
- pH
- Protein
- Specific Gravity
- Urobilinogen
- Microscopic Examinations (abnormalities on any of the following 3 dipstick results: leukocyte esterase, blood, or nitrite, and if judged clinically significant by the Investigator)

Immunochemistry

- T4 (free)
- T3 (free)
- TSH
- FSH
- AFP
- IL-6ha
- TNF-alpha hs

All laboratory data collected at scheduled and unscheduled visits will be included in the listings, but only results collected as scheduled visits will be included in the summary tables.

Results for individual parameters may be reported in different units depending on the analyzing laboratory. If required, the results (and the corresponding normal range cut-off values) for individual parameters may be converted to International System of Units (S.I.) units to summarize the data.

For all the parameters where a unit value has been reported, the parameter names that will be used in the outputs will comprise of the test name and the unit of measure, for example, 'Albumin (g/L)'. For the urinalysis parameters, the parameter name will be the reported test name only. Parameters will be sorted alphabetically within tables and listings.

For all parameters where a normal range limit value was reported, the normal range will be derived based on the available lower and upper limit values and any reported mathematical symbols. If both a lower and upper limit value is available, the normal range will be presented as '(Lower, Upper)'.

The reported results for each parameter with a defined normal range will be classified ('Low', 'Normal', 'High') in relation to the defined normal range limits. If a result is equal to the normal range cut-off value, the result will be considered 'Normal'.

The hematology, coagulation, chemistry and lipid and metabolic profile results tables will present summary statistics for each laboratory parameter within the specific test panel. For each parameter, summaries will be presented for the baseline and each scheduled post-baseline visit. In addition, summaries will be presented for the change from baseline values (and % change from baseline for the lipid and metabolic profile results) at each scheduled post-baseline visit (continuous descriptive analysis).

The decimal precision to which the summaries for each parameter will be based on the maximum number of decimals to which the reported result or the normal range limits are presented to in the raw data. The results and normal ranges will be displayed to the same decimal precision in the listings.

Additionally, counts (%) of number participants with values out of normal range at each scheduled time point will also be presented along with shift tables that will represent the changes in normal range categories across post-baseline time points (categorical descriptive analysis).

For ALT, AST, Total Bilirubin, and GGT tests, individual (for each participant) actual and change from baseline values over time will be displayed graphically and box plots over time by treatment group will be generated as well. A summary of maximum CTCAE Grades for post treatment assessments will be produced. Also, the HBV DNA versus ALT and AST at each visit will be displayed graphically.

For Lipid parameters-total cholesterol, LDL-C, HDL-C and triglycerides, individual (for each participant) actual values over time will be displayed graphically.

The urinalysis table will present counts and percentages of normal, abnormal clinically significant and clinically significant for the reported results at baseline and each post-baseline visit for all parameters (categorical descriptive analysis).

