### 8.3. Drug-Induced Liver Injury

#### 8.3.1. Normal values at baseline

Drug-induced liver injury (DILI) monitoring in patients with **normal liver transaminases and bilirubin at baseline** should be performed throughout the study according to the procedures summarized below:

- If patients with normal baseline liver indices develop elevations of aspartate aminotransferase (AST) or alanine aminotransferase (ALT) >2 upper limit of normal (ULN) or total bilirubin (TBL) >1.5 ULN values during the study, repeat testing should be performed within 48 hours.
- If there are persistent elevations (ALT or AST >2 ULN or TBL >1.5 ULN) upon repeat testing, close observation (testing and physical examination 2 to 3 times per week) should be implemented. An important purpose of the close observation is to gather additional clinical information to seek other possible causes of the observed liver test abnormalities, such as 1 of the following: acute viral hepatitis, alcoholic and autoimmune hepatitis, hepatobiliary disorders, cardiovascular causes, or concomitant treatments. Discontinuation of study drug should be considered.

[figure not shown]
Study drug should be discontinued, and the patient should be followed until resolution of signs or symptoms, in the following situations:

- ALT or AST >8 ULN.
- ALT or AST >5 ULN for more than 2 weeks.
- ALT or AST >3 ULN and (TBL >2 ULN or international normalized ratio [INR] >1.5).
- ALT or AST >3 ULN with the appearance of fatigue, nausea, vomiting, right upper quadrant pain or tenderness, fever, rash, and/or eosinophilia (>5%).

For any patients who present with a constellation of syndromes indicative of liver disease as per the Investigator's overall assessment (i.e., fatigue, nausea, vomiting, right upper quadrant pain or tenderness, fever, rash, and/or eosinophilia [>5%]), perform liver function tests to determine if liver disease is worsening.

Re-initiation of study drug may be considered after consultation with the Medical Monitor.

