3.1 General Considerations

All data collected on the electronic case report form (eCRF) will be presented in the data listings and will be listed and sorted by treatment arm, participant number and visit, where applicable. All descriptive summaries will be presented by treatment group and nominal visit/time point (where applicable).

Unless otherwise stated, the following methods will be applied:

- Continuous variables: Descriptive statistics will include the number of non-missing values (n), arithmetic mean, standard deviation (SD), median, minimum and maximum values.

The minimum and maximum values will be displayed to the same decimal precision as the source data, the arithmetic mean, SD and median values will be displayed to one more decimal than the source data for the specific variable.

95% Confidence Intervals (CIs), mean differences (among treatments and from baseline) and least-square (LS-Means) values will be displayed to one more decimal than the source data for a specific variable. P-values will be displayed to 3 decimal places.

The appropriate precision for derived variables will be determined based on the precision of the data on which the derivations are based, and statistics will be presented in accordance with the above-mentioned rules.

- Figures based on continuous summary data:
 - X-axis will represent the linear scheduled time expressed as -Day x for screening values and +Day y on treatment values
 - Y-axis will represent the Mean (+/-SD) and be presented as box-plots (median interquartile) parameter value (unit).
- Categorical variables: Descriptive statistics will include counts and percentages per category. The denominator in all percentage calculations will be the number of participants in the relevant analysis population with non-missing data, unless specifically stated otherwise. Percentages will be displayed to one decimal place. Proportions will be displayed to 3 decimal places.

95% Confidence Intervals (CIs), difference in proportions, odds ratio's and other categorical parameters will be displayed to one decimal place for percentages. Proportions will be displayed to 3 decimal places. P-values will be displayed to 3 decimal places.

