- Repeat/unscheduled assessments: Only values collected at scheduled study visits/time points will be presented in summary tables. If a repeat assessment was performed, the result from the original assessment will be presented as the result at the specific visit/time point. All collected data will be included in the data listings.
- Assessment windows: All assessments will be included in the data listings and no visit windows will be applied to exclude assessments that were performed outside of the protocol specified procedure windows.
- Result display convention: Results will be center aligned in all summary tables and listings. Participant identifiers visit and parameter labels may be left-aligned if required.
- Date and time display conventions: The following display conventions will be applied in all outputs where dates and/or times are displayed:

Date only: YYYY-MM-DD

Date and time: YYYY-MM-DD HH:MM

If only partial information is available, unknown components of the date or time will be presented as 'NK' (not known), i.e., '2016-NK-NK'. Times will be reported in military time.

- End of Study (EoS) vs Early Termination (ET)

For any analyses based on safety data, efficacy and PD data, EOS and ET assessment will be summarized separately.

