Figure 14.3.4.2.11 Boxplot of ALP over Time by Treatment (Safety Set)..... 129

Figure 14.3.4.2.12 Individual GGT over Time (Safety Set)..... 130

Figure 14.3.4.2.13 Individual GGT Change from Baseline (Safety Set)..... 131

Figure 14.3.4.2.14 Boxplot of GGT over Time by Treatment (Safety Set)..... 132

Figure 14.3.4.2.15 Individual Total Bilirubin over Time (Safety Set)..... 133

Figure 14.3.4.2.16 Individual Total Bilirubin Change from Baseline (Safety Set)..... 134

Figure 14.3.4.2.17 Boxplot of Total Bilirubin over Time by Treatment (Safety Set)..... 135

Figure 14.3.4.2.18 Individual Lipid Parameters over Time (Safety Set)..... 136

Figure 14.3.4.2.19 Individual HBV DNA versus ALT at Each Visit (Safety Set)..... 137

Figure 14.3.4.2.20 Individual HBV DNA versus AST at Each Visit (Safety Set)..... 138

GENERAL COMMENTS

- Where a count is 0, the percentage will not be shown (e.g. 0(0.0%) will be displayed as 0)
- Unless otherwise states, parameters will be listed in alphabetical order.
- The minimum and maximum values will be presented to the same number of decimal places as recorded in the electronic Case Report Form (eCRF)
- Mean, SD, and Median will be presented to one more decimal place than the raw data
- Percentages will be rounded to one decimal place, with the denominator being the number of subjects in the relevant population with non-missing data, unless otherwise specified
- Change from Baseline:
Change from Baseline will be calculated as:
Change from Baseline = post baseline value – baseline value
- Unscheduled visits will be excluded from summary tables but included in all by-participant listings.
- **Names and order of Treatment Groups for Table Summaries**
 - Group 1 = EYP001a 200 mg QD + NA daily
 - Group 2 = EYP001a 200 mg QD + NA daily HBeAg+
 - Group 3 = EYP001a 200 mg QD + NA daily HBeAg-
 - Group 4 = Placebo + NA daily
 - Group 5 = Placebo HBeAg+
 - Group 6 = Placebo HBeAg-
 - Group 7 = All HBeAg+
 - Group 8 = All HBeAg-
 - Group 9 = All Study Patients

• **Treatment Display by Page**

Page 1, 3, 5, etc.

EYP001a 200 mg QD + NA daily (N=xx)	= EYP001a 200 mg QD + NA daily HBeAg+ (N=xx)	= EYP001a 200 mg QD + NA daily HBeAg- (N=xx)	Placebo + NA daily (N=xx)
---	--	--	------------------------------

Page 2, 4, 6, etc.

Placebo HBeAg+ (N=xx)	Placebo HBeAg- (N=xx)	All HBeAg+ (N=xx)	All HBeAg- (N=xx)	All Study Patients (N=xx)

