[1] Baseline is defined as the last available, valid, non-missing observation prior to first study drug administration. Number of participants at each visit (n) will be used as the denominator for the calculation of all percentages.

Table 14.3.4.4 Summary of Maximum CTCAE for ALT, AST, BILI and GGT for Post Treatment Assessments (*Safety Set*)

Parameters/ grade	Group 1 (N=XXX)	etc.	Group x (N=XXX)
Number of subjects with any CTCAE	xx (xx.x%)	xx (xx.x%)	xx (xx.x%)
ALT			
No CTCAE (Grade 0)	xx (xx.x%)	xx (xx.x%)	xx (xx.x%)
Grade 1	xx (xx.x%)	xx (xx.x%)	xx (xx.x%)
Grade 2	xx (xx.x%)	xx (xx.x%)	xx (xx.x%)
Grade 3	xx (xx.x%)	xx (xx.x%)	xx (xx.x%)
Grade 4	xx (xx.x%)	xx (xx.x%)	xx (xx.x%)
Grade 5	xx (xx.x%)	xx (xx.x%)	xx (xx.x%)

< repeat for AST, BILI and GGT >

Etc.

Source: Listing 16.2.8.2.1

This table is based on maximum grading using CTCAE version 5.0

BILI = Total Bilirubin; GGT= Gamma Glutamyl Transferase; ALT =Alanine Aminotransferase; AST = Aspartate Aminotransferase

Table 14.3.5.1 Summary of Vital Signs (Safety Set)

Parameter: Heart rate (beats/min)

Visit Statistics	Group 1 (N=XXX)		etc.		Group x (N=XXX)	
	Actual Value	Change from Baseline	Actual Value	Change from Baseline	Actual Value	Change from Baseline
Baseline [1]						
N	XX	N/A	XX	N/A	XX	N/A
Mean	XX	N/A	XX	N/A	XX	N/A
SD	XX	N/A	XX	N/A	XX	N/A
Median	XX	N/A	XX	N/A	XX	N/A
Minimum	XX	N/A	XX	N/A	XX	N/A
Maximum	XX	N/A	XX	N/A	XX	N/A
Week 2						
N	XX	XX	XX	XX	XX	XX
Mean	XX	XX	XX	XX	XX	XX
SD	XX	XX	XX	XX	XX	XX
Median	XX	XX	XX	XX	XX	XX
Minimum	XX	XX	XX	XX	XX	XX
Maximum	XX	XX	XX	XX	XX	XX
Week xx						
n	XX	XX	XX	XX	XX	XX
Mean	XX	XX	XX	XX	XX	XX
SD	XX	XX	XX	XX	XX	XX
Median	XX	XX	XX	XX	XX	XX
Minimum	XX	XX	XX	XX	XX	XX
Maximum	XX	XX	XX	XX	XX	XX

Source: Listing 16.2.9.1

[1] Baseline is defined as the last available, valid, non-missing observation prior to first study drug administration.
 N/A = Not Applicable. SD = Standard Deviation.

Table 14.3.5.2.1 Summary of 12-Lead ECG (Safety Set)

Parameter: Heart Rate (bpm)

Visit Statistics	Group 1 (N=XXX)		etc.		Group x (N=XXX)	
	Actual Value	Change from Baseline	Actual Value	Change from Baseline	Actual Value	Change from Baseline
Baseline [1]						
N	XX	N/A	XX	N/A	XX	N/A
Mean	XX	N/A	XX	N/A	XX	N/A
SD	XX	N/A	XX	N/A	XX	N/A
Median	XX	N/A	XX	N/A	XX	N/A
Minimum	XX	N/A	XX	N/A	XX	N/A
Maximum	XX	N/A	XX	N/A	XX	N/A
Week xx						
N	XX	XX	XX	XX	XX	XX
Mean	XX	XX	XX	XX	XX	XX
SD	XX	XX	XX	XX	XX	XX
Median	XX	XX	XX	XX	XX	XX
Minimum	XX	XX	XX	XX	XX	XX
Maximum	XX	XX	XX	XX	XX	XX

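### SAP Table 14.3.4.4 (maximum CTCAE liver grade) is bound by the scheduled-visits-only rule, so the worst grade by arm can be too low when a repeat test under Protocol 8.3 records the peak

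*SAP*

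**What the plan says.** Three places in the SAP keep unscheduled results out of summary tables.

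- SAP 3.1, General Considerations: "Only values collected at scheduled study visits/time points will be presented in summary tables". It then settles repeats in favour of the first value: "If a repeat assessment was performed, the result from the original assessment will be presented as the result at the specific visit/time point". Both rules stand under the lead-in "Unless otherwise stated, the following methods will be applied", so an exception has to be written down.
- SAP 13.2, Safety Laboratory Assessments: "only results collected as scheduled visits will be included in the summary tables".
- Mock shells, General Comments: "Unscheduled visits will be excluded from summary tables but included in all by-participant listings".

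The maximum-grade output is announced later in SAP 13.2: "A summary of maximum CTCAE Grades for post treatment assessments will be produced". SAP 15 lists it as an addition to the protocol. The shell for Table 14.3.4.4 is titled as a summary, and its footnote gives only the grading version: "This table is based on maximum grading using CTCAE version 5.0". None of these places mentions unscheduled or repeat results. SAP 18 marks the table for the DSMC Safety and Futility meeting.

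For patients with normal baseline values, Protocol 8.3.1 says that after ALT or AST exceeds 2 x ULN, or bilirubin exceeds 1.5 x ULN, "repeat testing should be performed within 48 hours". If the elevation persists, testing moves to 2 to 3 times a week. Protocol 8.3.2 has the same sequence, relative to baseline, for patients with elevated baseline values.

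**The concern.** A scheduled-only rule is sensible for by-visit means and shift tables, where each patient should contribute one value per visit. It does not suit a maximum, whose purpose is to capture the worst value seen. In a patient whose liver tests are rising, Protocol 8.3 makes the off-schedule tests the densest source of data around the peak, and those are the results the rule removes.

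The table shows counts of liver grade by arm to the DSMC at a Go/No-go meeting, and later to readers of the study report. Adding results to a maximum can raise it but never lower it, so any error from leaving them out goes one way. Numbers are small. SAP 15 says enrolment was suspended after about 25 randomizations. At 3:1 that is about 25 x 0.75 = 19 patients on EYP001a, so one misgraded patient moves that arm's rate by 1/19, about 5 percentage points.

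**Working it through.** The plan states no figure to reproduce, because this is a rule about which data enter a table. The check has three steps.

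**1. Is there an exception?** The SAP does say so when it wants off-schedule data. SAP 3.2 admits repeat and unscheduled assessments to the general baseline definition, and the programming notes for the individual ALT, AST, ALP, GGT and bilirubin plots put scheduled and unscheduled time on the x-axis. No such wording appears for Table 14.3.4.4.

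**2. How many results are excluded?** Tests under close observation = (gap in days / 7) x 2 to 3 per week.

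- 14-day treatment gap: 14/7 x 2 = 4, to 14/7 x 3 = 6 unscheduled tests. With the two scheduled visits at either end, 4/6 = 67% to 6/8 = 75% of results are excluded.
- 84-day gap, Week 28 to Week 40: 24 to 36 tests. This is an upper bound, because Protocol 8.3.3 lets the frequency fall to weekly or less.

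These are shares of results, not probabilities that a peak is lost. Protocol 8.3.3 names ALT, AST, alkaline phosphatase and bilirubin for the repeats. GGT is in the table but not in that list.

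**3. How often would a recorded Grade 3 value be dropped?** The documents give no flare kinetics, so everything here is assumed:

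- Grade 3 begins above 5 x ULN, and baseline is normal.
- The true peak P is log-uniform from 5 to 10 x ULN (or 5 to 20).
- ALT at day s is P x 2^(-|s - t|/h), with h = 7 or 14 days.
- The peak day t is uniform over a visit gap of G days.
- If the scheduled value before the peak exceeds 2 x ULN, a repeat follows on day 2 and then every 3 days.

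First, the share in which both adjacent scheduled values are at or below 5 x ULN. The nearer visit lies d days from the peak, with d uniform on 0 to G/2, so the share is the probability that log2(P/5) is at most d/h. For peaks of 5 to 10, log2(P/5) is uniform on 0 to 1:

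- G = 14, h = 7: d/h is uniform on 0 to 1, giving 1/2 = 50%.
- G = 14, h = 14: d/h is uniform on 0 to 0.5, giving its mean, 25%.
- G = 84, h = 7: d/h is uniform on 0 to 6, giving 1 - (1/6)(1/2) = 92%.
- G = 84, h = 14: d/h is uniform on 0 to 3, giving 1 - (1/3)(1/2) = 83%.

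Second, the share that the SAP rule itself loses. This also requires that the preceding visit triggered repeats and that one of them exceeded 5 x ULN. Simulation with 400,000 draws per cell gives:

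| Gap | Peak (x ULN) | h (days) | Missed by scheduled visits | Recorded on a repeat, then dropped |
|---|---|---|---|---|
| 14 days | 5 to 10 | 7 | 50% | 37% |
| 14 days | 5 to 10 | 14 | 25% | 20% |
| 14 days | 5 to 20 | 7 | 25% | 19% |
| 14 days | 5 to 20 | 14 | 12% | 10% |
| 84 days | 5 to 10 | 7 | 92% | 10% |
| 84 days | 5 to 10 | 14 | 83% | 21% |

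The last column measures the rule. In the 84-day gap, 88% (h = 7) and 74% (h = 14) of the missed peaks had no triggering value at the visit before, so no repeat tests were running.

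**The case against.** The strongest reply is that nothing is lost from the report. Listing 16.2.8.2.1 holds unscheduled results, prints the CTCAE grade for ALT, AST, bilirubin and GGT, and goes to the same DSMC meeting. So do the individual ALT, AST and bilirubin plots, one page per treatment group, and the stopping-rules listing, which covers the Section 8.3 discontinuation criteria. With about 25 patients, a committee could count grades from the listing. Abnormalities judged clinically significant are recorded as AEs under Protocol 8.1.5, graded by CTCAE, and so reach the TEAE severity tables by arm. Finally, the maximum-grade sentence does not itself say scheduled, and the shell names Listing 16.2.8.2.1 as its source, so a programmer might include everything.

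Much of this stands, and it limits the consequence. It does not remove the point. A listing or plot gives no tabulated count by arm, and the TEAE route depends on the investigator's judgement of significance. A missing word does not override three explicit rules, and a programmer left to guess is itself a reason to specify.

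Three stronger readings should be resisted:

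- A reader might infer that the worst grade is always understated. It is understated only when a repeat or unscheduled value outgrades every scheduled one.
- A reader might infer that 83% to 92% of follow-up peaks are lost to the rule. Most of that share reflects sparse visits, and changing the SAP would not recover it.
- A reader might infer that a drug effect on the liver is hidden. The graded listing, the plots and the AE tables keep the events visible. What the documents support is that one descriptive count by arm may be too low.

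**Conclusion.** The point holds as a one-directional defect in one table. Followed as written, the SAP computes a maximum liver grade without the repeat and unscheduled tests that Protocol 8.3 generates for ALT, AST and bilirubin. Table 14.3.4.4 is the only table that grades laboratory liver results directly by arm, and the second DSMC meeting receives it.

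That the bias can only be downward follows from the text and needs no assumption. Its size does need assumptions. Under the kinetics above, a recorded Grade 3 value would be dropped in about 20% to 37% of patients with peaks of 5 to 10 x ULN on the 2-weekly schedule (10% to 19% with peaks up to 20 x ULN), and in about 10% to 21% in the 12-week follow-up gap. These are shares of patients who have such a peak, not of all patients. The documents give no basis for how many that will be. The change should be made, but the trial's safety oversight does not rest on this table alone.

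**What to change.** In SAP 3.1, SAP 13.2, the mock-shell General Comments and the footnote to Table 14.3.4.4, state that the maximum CTCAE grade uses every result after the first dose, whether scheduled, repeat or unscheduled. In the same sentence, define the post-treatment period named in the table title as starting at first dose, since it could also be read as after the end of treatment. Keep the scheduled-only rule for by-visit summaries and shift tables.

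The cost is one sentence and one programming filter, with no new data. The drawback is that patients tested more often have more chances of a higher grade; a footnote to the table should say so.
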